## **Title**

Randomized, cross-over study comparing the effect of two alcohol-free beers with different carbohydrates composition on lipid and glycemic metabolism in subjects with prediabetes and recently diagnosed diabetes and overweight or obesity.

**Brief title:** Effect of two alcohol-free beers with different carbohydrates composition on lipids and glucose metabolism.

## **Objective:**

**Primary:** To determine the effect of an alcohol-free beer with low glycemic index carbohydrates (isomaltulose) and a resistant maltodextrin, comparing to an alcohol-free beer with regular composition, on glycemic metabolism (glucose, glycated hemoglobin, insulin and HOMA index) in subjects with recently diagnosed diabetes mellitus and overweight or obesity.

**Secondary:** To determine the effect of an alcohol-free beer with low glycemic index carbohydrates (isomaltulose) and a resistant maltodextrin, comparing to an alcohol-free beer with regular composition, on: a) lipid profile (total cholesterol, LDL cholesterol, HDL cholesterol, triglycerides and apolipoproteins A and B); b) body weight and waist circumference; c) inflammatory biomarkers (C reactive protein); d) intestinal microbiota in a subgroup of participants.

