## **Inclusion criteria:**

- Aged between 18 and 80 years.
- To provide informed consent in writing of voluntary participation in the study after having read the participant information sheet, and having consulted the doubts that may arise from it.
- Diagnosis of prediabetes or diabetes mellitus type 2 defined as: a) fasting glucose  $\geq 100$  mg/dL in the last 3 months; b) glycated hemoglobin  $\geq 5.7\%$  and  $\leq 6.5\%$ .

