### **Brief Summary:**

This a controlled, double-blind, randomized, cross designed study to determine the effect of an alcohol-free beer with low glycemic index carbohydrates (isomaltulose) and a resistant maltodextrin, comparing to an alcohol-free beer with regular composition, on glycemic metabolism (glucose, glycated hemoglobin, insulin and HOMA index) in subjects with recently diagnosed diabetes mellitus and overweight or obesity. We include 44 subjects who are randomized to consume for 10 weeks: a) two alcohol-free beers with regular carbohydrates composition per day; b) two alcohol-free beers with modified carbohydrates composition per day. Those subjects randomized to begin with A beer

during 10 weeks will change to B beer during the second phase for 10 weeks and vice versa. There is a 4-8 weeks wash-out period between two phases.

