### **Study visits:**

1. Prescreening visit: Inclusion and exclusion criteria assessment and blood collection if glucose or glycated hemoglobin is not available in previous 3 months. Healthy dietary and physical activity counselling is provided by a nutritionist; it should be maintained during all study. Baseline visit is scheduled in 2-4 weeks after lifestyle stabilization.

2. Baseline phase 1 visit: Clinical, biochemical, dietary, physical activity and anthropometric data are assessed. Computer-based randomization is performed. Alcohol-free beer (A or B according to randomization procedures) for the next 10 weeks is delivered to the participant who has to consume two per day. A nutritionist emphasizes healthy lifestyle counselling to the participant. A feces sample is collected if subjects accept to be included in microbiota sub study.
3. Intermediate phase 1 visit: Clinical, biochemical, dietary, physical activity and anthropometric data are assessed. Satiety after alcohol-free beer consumption is measured by a validated questionnaire. A nutritionist emphasizes healthy lifestyle counselling to the participant.
4. End of phase 1 visit: Clinical, biochemical, dietary, physical activity and anthropometric data are assessed. Satiety after alcohol-free beer consumption is measured by a validated questionnaire. A nutritionist emphasizes healthy lifestyle counselling to the participant. A wash-out period of 4-8 weeks is scheduled before the next phase start. A feces sample is collected if subjects accept to be included in microbiota sub study.
5. Baseline phase 2 visit: Clinical, biochemical, dietary, physical activity and anthropometric data are assessed. Alcohol-free beer (A or B: if subjects consumed alcohol-free beer A, he/she change to alcohol-free B and vice versa) for the next 10 weeks is delivered to the participant who has to consume two per day. A nutritionist emphasizes healthy lifestyle counselling to the participant. A feces sample is collected if subjects accept to be included in microbiota sub study.
6. Intermediate phase 2 visit: Clinical, biochemical, dietary, physical activity and anthropometric data are assessed. Satiety after alcohol-free beer consumption is measured by a validated questionnaire. A nutritionist emphasizes healthy lifestyle counselling to the participant.

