### **Statistical analysis plan**

The sample size was established by taking as main outcome variable the change of glucose concentration, whose clinical variability is estimated at 16 mg/dL in pre-diabetic population. This is the estimated value based on the epidemiological study carried out in Spanish population (PREDIMED) (Estruch R et al. N Engl J Med 2013;368:1279-90). It was expected to find a difference of 12 mg/dL in glucose levels between two intervention

arms. It was established a confidence level ( $1-\alpha$ ) of 95% (bilateral  $Z\alpha = 1,960$ ) and 90% of statistical power ( $1 - \beta$ ) (bilateral  $Z\beta = 1,282$ ), by obtaining a sample size of 37 subjects. It was estimated a 25% loss rate, so final sample was 44 subjects.

Different alcohol-free beers effects on study outcomes will be evaluated by repeated measures ANOVA or the Friedman test, as appropriate. When significant differences are detected, multiple comparisons will be made by using the Bonferroni correction for normally distributed variables or the Wilcoxon test for paired samples for variables with a skewed distribution. Treatment order will be entered in all models as an additional factor. Data will be presented as means ( $\pm$ SD) for continuous variables or medians and interquartile ranges (IR) for those with a skewed distribution). Statistical analysis will be processed using the software SPSS (version 24.0; SPSS, Chicago, Illinois, USA), using a significance level of  $P < 0,05$ .

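### The primary objective lists four unranked glycemic measures; the choice of glucose as main outcome is made for the sample size but not carried through to the objective or the analysis

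*Combined protocol and SAP*

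**What the plan says.** The Objective section gives one primary objective: the effect of the modified beer against the regular one "on glycemic metabolism (glucose, glycated hemoglobin, insulin and HOMA index"). The Brief Summary repeats it: "comparing to an alcohol-free beer with regular composition, on glycemic metabolism (glucose, glycated hemoglobin, insulin and HOMA index"). Neither place ranks the four measures. The secondary objective is a separate list (lipids and apolipoproteins, weight and waist, C reactive protein, microbiota), and HbA1c, insulin and HOMA are not in it.

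The Statistical analysis plan section sets the sample size by "taking as main outcome variable the change of glucose concentration". The planning difference is also in glucose alone: "It was expected to find a difference of 12 mg/dL in glucose levels between two intervention" arms.

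The analysis paragraph of that section does not use the designation again: "Different alcohol-free beers effects on study outcomes will be evaluated by repeated measures ANOVA or the Friedman test, as appropriate". One significance level, P<0.05, applies throughout. The only multiplicity provision is this: "When significant differences are detected, multiple comparisons will be made by using the Bonferroni correction for normally distributed variables", with the Wilcoxon test for skewed variables.

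The section does not say which visits give the change in glucose. Under Study visits, biochemistry is taken at the baseline and end visits of each phase and also in between, for example "Intermediate phase 1 visit: Clinical, biochemical, dietary, physical activity and anthropometric data are assessed".

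**The concern.** A reader of the Objective section sees four measures of equal standing under the word primary. A reader of the sample-size paragraph sees one. The analysis paragraph does not settle the matter, because it treats every outcome the same way. A significant result on insulin or HbA1c alone, with glucose not significant, could therefore be reported as meeting the primary objective without breaking any sentence of the plan.

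The Bonferroni step does not prevent this. It follows a significant overall test and covers the comparisons made within one outcome; it does not act across the four measures.

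What is at stake is the meaning of the 95% confidence level used for planning. It holds for a conclusion decided by glucose. It does not hold for a conclusion that any one of four measures may decide.

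**Working it through.** **1. The plan's own figure.** Inputs from the Statistical analysis plan section: difference 12 mg/dL, variability 16 mg/dL, Z values 1.960 and 1.282.

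n = 2 × (16 × (1.960 + 1.282) / 12)² = 2 × (4.3227)² = 37.37

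The plan states 37, so the figure reproduces. Power with 37 by the same formula is 89.7%, against the stated 90%. Every input is a glucose figure; the other three measures play no part in the sizing.

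**2. Error if glucose alone decides.** One two-sided test at 0.05: 5%.

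**3. Error if any one of the four may decide.** The documents give no correlations among the four measures and no SDs for HbA1c, insulin or HOMA, so these are assumptions:

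- One between-beer test per outcome, two-sided at 0.05, with no true difference between the beers.
- HOMA in its usual form, a product of glucose and insulin up to a constant, so that log HOMA = log glucose + log insulin + constant. The plan gives no formula.
- A common correlation r among glucose, insulin and HbA1c.
- Log-scale SDs for glucose/insulin of 0.12/0.45, 0.12/0.30, 0.15/0.25, 0.20/0.20 and 0.08/0.50.

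The HOMA statistic is then z_HOMA = (s_g·z_g + s_i·z_i) / √(s_g² + s_i² + 2r·s_g·s_i), where s_g and s_i are the two SDs. The error is the share of simulated trials (2,000,000 draws) in which any of the four |z| exceeds 1.96. The excess is the share in which that happens while glucose is not significant. Because glucose on its own contributes 5%, the excess is the error minus 5 points.

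| Assumed r | Any of four significant | Of which glucose not significant |
|---|---|---|
| 0 | 14.8–15.9% | 9.8–10.9 points |
| 0.3 | 14.0–14.5% | 9.0–9.5 points |
| 0.6 | 12.0–12.1% | 6.9–7.1 points |
| 0.8 | 9.9% | 4.9 points |
| 0.9 | 8.4% | 3.4 points |

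The ranges within a row come from the five SD pairs.

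**4. Check at the trial's size.** A crossover test with treatment order in the model (n − 2 degrees of freedom; SDs 0.12/0.45) gives 15.1%, 14.1%, 12.0% and 10.0% at r = 0, 0.3, 0.6 and 0.8 with n = 37. With n = 33 (44 × 0.75) it gives 15.2%, 14.3%, 12.0% and 9.9%. Small-sample effects do not change the picture.

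**The case against.** The strongest reply is that the plan already answers the question. It calls change in glucose the main outcome variable, and the difference, variability, power and sample size all rest on it. An objective may name a domain and its measures while the statistical section picks one of them as the main outcome; that is not a contradiction. No passage calls HbA1c, insulin or HOMA a primary or co-primary outcome, and none states an any-of-four rule. All of this stands. The gap is that the designation is not carried through, and the error figures are conditional on a rule that the documents neither state nor exclude.

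The reply does not close the gap. The phrase occurs once, as the basis for sizing, and the three other measures appear under the primary heading and nowhere in the secondary list.

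Two stronger readings are tempting. A reader might infer that the trial's primary error rate is in fact inflated. The documents do not support that, because under the most natural reading it is 5%. A reader might also treat the four tests as independent and compute 1 − 0.95⁴. That case cannot arise when HOMA is built from glucose and insulin, and it overstates the size.

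It is also fair to say that a stated multiplicity rule across the four would close the gap without demoting any measure. It would cost more. At 0.05/4 = 0.0125 per test the plan's formula gives 51 in place of 38 (37.37 rounded up), and power for glucose with 37 falls to 76.7%.

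**Conclusion.** The point holds as a gap in the text. The plan chooses glucose for sizing but does not say, in the objective or in the analysis paragraph, that glucose alone decides the primary conclusion. If it does, the error is 5% and the plan is sound here. If any of the four may decide, the error is about 8% to 16%, with an excess of about 3 to 11 points made up wholly of trials in which glucose is not significant. That range rests on assumed correlations from 0.9 to 0, assumed SDs, HOMA built from glucose and insulin, and one test per outcome.

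The unstated visits for the change are a matter of clarification. None of the error figures concerns them.

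Rating: cheap improvement.

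**What to change.** In the Objective, Brief Summary and Statistical analysis plan sections, state: *The single primary outcome is the between-beer difference in change of glucose from [visit] to [visit] of each phase, tested at two-sided 0.05. HbA1c, insulin and HOMA are secondary and cannot on their own support the primary conclusion.* The sponsor fills in the visits. This adopts the choice that the plan already makes for its sample size.

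Cost: a result on HbA1c, insulin or HOMA alone can no longer be claimed as primary. The sample size (44), the visit schedule and the power for glucose are unchanged.

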## **Inclusion criteria:**

- Aged between 18 and 80 years.
- To provide informed consent in writing of voluntary participation in the study after having read the participant information sheet, and having consulted the doubts that may arise from it.
- Diagnosis of prediabetes or diabetes mellitus type 2 defined as: a) fasting glucose  $\geq 100$  mg/dL in the last 3 months; b) glycated hemoglobin  $\geq 5.7\%$  and  $\leq 6.5\%$ .

### **Exclusion criteria:**

- Gluten intolerance.
- Taking lipid-lowering drugs.
- Taking antidiabetic drugs, except for metformin in a stable dose in the last 3 months.
- To be under treatment with insulin.
- Presence of uncontrolled endocrinological disease by including hypothyroidism.
- Regular intake of functional foods with plant sterols in the past 6 weeks.
- Intake of vitamin supplements.
- Hormone replacement therapy.
- High intake of alcohol (> 30 g ethanol) on a regular basis.
- Pregnancy or intention of pregnancy during the study since the proposed nutritional intervention may not be suitable for this situation.
- Serious illness of any type with less than 1-year life expectancy or if, in the opinion of the investigators, it would limit a stable diet throughout the study.
- To be under treatment with corticosteroids, hormonal treatment or antibiotics the 3 months prior to randomization.
- To take prebiotics, probiotics, vitamin supplements and any other drug that could influence the intestinal microbiota, in the 3 months prior to randomization.
- Any other circumstances which, according to researcher's assessment, could interfere with the correct development of nutritional intervention (e.g.: frequent trips during the study, failure to attend visits by personal or business circumstances, etc.).

### **Brief Summary:**

This a controlled, double-blind, randomized, cross designed study to determine the effect of an alcohol-free beer with low glycemic index carbohydrates (isomaltulose) and a resistant maltodextrin, comparing to an alcohol-free beer with regular composition, on glycemic metabolism (glucose, glycated hemoglobin, insulin and HOMA index) in subjects with recently diagnosed diabetes mellitus and overweight or obesity. We include 44 subjects who are randomized to consume for 10 weeks: a) two alcohol-free beers with regular carbohydrates composition per day; b) two alcohol-free beers with modified carbohydrates composition per day. Those subjects randomized to begin with A beer

during 10 weeks will change to B beer during the second phase for 10 weeks and vice versa. There is a 4-8 weeks wash-out period between two phases.

### **Study Detailed Description:**

The study involves a nutritional intervention with a controlled, double-blind, randomized, cross design. It includes 44 healthy subjects with a total duration of 20 weeks with a "wash-out/stabilization" period for 2-4 weeks before randomization. Subjects are randomized in two groups: (1) those who begin drinking 2 alcohol-free beers (33 cl each one) that are enriched in a resistant maltodextrin and isomaltulose during 10 weeks and continue drinking 2 alcohol-free beers (33 cl each one) with regular composition during the next 10 weeks following; (2) those who will follow the same previous intervention but in reverse, beginning with standard alcohol-free beer for 10 weeks, followed by resistant maltodextrin and isomaltulose-enriched beer for the remaining 10 weeks. There is a washout period between both phases to facilitate adherence to nutritional intervention, since we consider that a period of 20 consecutive weeks could be difficult to assume for the participants. Participants and the research team are "blind" to the type of beer that subjects are taking in each phase. Only one person of the company that provide beers, which does not directly participate in the clinic visits or in the analysis of the data, is aware of this information. Clinical staff performed the randomization based on a computerized method.

Among those subjects included in the study, microbiota sub-study is proposed which require a specific authorization within informed consent. Among all subjects that are included in this substudy and that have completed the whole nutritional intervention, 10 subjects (5 from each randomized group) will be selected to microbiota determination.

### **Study visits:**

1. Prescreening visit: Inclusion and exclusion criteria assessment and blood collection if glucose or glycated hemoglobin is not available in previous 3 months. Healthy dietary and physical activity counselling is provided by a nutritionist; it should be maintained during all study. Baseline visit is scheduled in 2-4 weeks after lifestyle stabilization.

2. Baseline phase 1 visit: Clinical, biochemical, dietary, physical activity and anthropometric data are assessed. Computer-based randomization is performed. Alcohol-free beer (A or B according to randomization procedures) for the next 10 weeks is delivered to the participant who has to consume two per day. A nutritionist emphasizes healthy lifestyle counselling to the participant. A feces sample is collected if subjects accept to be included in microbiota sub study.
3. Intermediate phase 1 visit: Clinical, biochemical, dietary, physical activity and anthropometric data are assessed. Satiety after alcohol-free beer consumption is measured by a validated questionnaire. A nutritionist emphasizes healthy lifestyle counselling to the participant.
4. End of phase 1 visit: Clinical, biochemical, dietary, physical activity and anthropometric data are assessed. Satiety after alcohol-free beer consumption is measured by a validated questionnaire. A nutritionist emphasizes healthy lifestyle counselling to the participant. A wash-out period of 4-8 weeks is scheduled before the next phase start. A feces sample is collected if subjects accept to be included in microbiota sub study.
5. Baseline phase 2 visit: Clinical, biochemical, dietary, physical activity and anthropometric data are assessed. Alcohol-free beer (A or B: if subjects consumed alcohol-free beer A, he/she change to alcohol-free B and vice versa) for the next 10 weeks is delivered to the participant who has to consume two per day. A nutritionist emphasizes healthy lifestyle counselling to the participant. A feces sample is collected if subjects accept to be included in microbiota sub study.
6. Intermediate phase 2 visit: Clinical, biochemical, dietary, physical activity and anthropometric data are assessed. Satiety after alcohol-free beer consumption is measured by a validated questionnaire. A nutritionist emphasizes healthy lifestyle counselling to the participant.
7. End of phase 2 visit: Clinical, biochemical, dietary, physical activity and anthropometric data are assessed. Satiety after alcohol-free beer consumption is measured by a validated questionnaire. A nutritionist emphasizes healthy lifestyle counselling to the participant. A feces sample is collected if subjects accept to be included in microbiota sub study.

### **Study variables:**

- Clinical variables: Gender, age, medical records including diseases and medication, tobacco consumption and blood pressure.
- Anthropometric variables: Weight, height, body mass index, waist circumference, body composition analysis.
- Biochemical variables: Glucose, lipid and iron metabolism are assessed. Inflammatory biomarkers, including C reactive protein, are also determined.
- Microbiota: Feces samples are collected to microbiota analysis including *Bacteroides*, *Lactobacillus*, *Enterococcus*, *Prevotella* or *Roseburia*, among others.
- Dietary and physical activity assessment: Diet and physical activity are assessed by validated questionnaires.

### **Informed consent**

All participants must sign a consent before entering the study. Informed consent is obtained by one of the researchers of the study after the patient has carefully reviewed the information sheet which explains the objectives, methodology, benefits and disadvantages of intervention. The participant is encouraged to ask for any doubt he/she has regarding the study before signing the informed consent. Informed consent includes a section where participant has to indicate if he/she wants to participate in the microbiota substudy. If they do not accept, they are included in the study if meeting eligibility criteria, but feces samples are not collected in corresponding visits.

The study, including protocol, informed consent, information sheet and other documents, has been approved by the Ethical Committee of Clinical Research of Aragon (CEICA).

### **Statistical analysis plan**

The sample size was established by taking as main outcome variable the change of glucose concentration, whose clinical variability is estimated at 16 mg/dL in pre-diabetic population. This is the estimated value based on the epidemiological study carried out in Spanish population (PREDIMED) (Estruch R et al. N Engl J Med 2013;368:1279-90). It was expected to find a difference of 12 mg/dL in glucose levels between two intervention

arms. It was established a confidence level ( $1-\alpha$ ) of 95% (bilateral  $Z\alpha = 1,960$ ) and 90% of statistical power ( $1 - \beta$ ) (bilateral  $Z\beta = 1,282$ ), by obtaining a sample size of 37 subjects. It was estimated a 25% loss rate, so final sample was 44 subjects.

Different alcohol-free beers effects on study outcomes will be evaluated by repeated measures ANOVA or the Friedman test, as appropriate. When significant differences are detected, multiple comparisons will be made by using the Bonferroni correction for normally distributed variables or the Wilcoxon test for paired samples for variables with a skewed distribution. Treatment order will be entered in all models as an additional factor. Data will be presented as means ( $\pm$ SD) for continuous variables or medians and interquartile ranges (IR) for those with a skewed distribution). Statistical analysis will be processed using the software SPSS (version 24.0; SPSS, Chicago, Illinois, USA), using a significance level of  $P < 0,05$ .

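### The glucose outcome is named as a change but its analysis is not defined; read as change from each phase's baseline, it is less precise than an end-of-phase contrast adjusted for the phase baselines.

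*Combined protocol and SAP*

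**What the plan says.** The Statistical analysis plan sets the sample size by "taking as main outcome variable the change of glucose concentration", with a variability of 16 mg/dL. It gives no reference point for the change. The target is worded in terms of levels: "It was expected to find a difference of 12 mg/dL in glucose levels" between the two arms.

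The analysis paragraph reads: "Different alcohol-free beers effects on study outcomes will be evaluated by repeated measures ANOVA or the Friedman test, as appropriate". The only further model term is order: "Treatment order will be entered in all models as an additional factor". No dependent variable, visit or baseline term is named.

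Under Objective, the primary aim concerns the effect "on glycemic metabolism (glucose, glycated hemoglobin, insulin and HOMA index"), with no time point. Under Study visits, biochemistry is taken at baseline, at an intermediate visit and at the end of each 10-week phase, so six times in all. Phase 2 has its own baseline, taken after the washout.

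**The concern.** The word change, together with a baseline visit in each phase, points to change from each phase's own baseline. Subtracting the baseline in full is efficient only when the baseline difference predicts the end-of-phase difference almost one for one. When the link is weaker, subtraction adds the baseline's noise to the contrast. A regression lets the data set the weight and uses the same measurements.

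The stake is precision for the variable on which the trial was sized. A second stake is that the plan should say in advance which single contrast answers the primary question. Validity is not at issue: for glucose, change and end-of-phase values are both legitimate outcomes.

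**Working it through.** **Inputs from the Statistical analysis plan.** Variability 16 mg/dL, target 12 mg/dL, two-sided 5%, power 90%, 37 evaluable subjects, 44 recruited, 25% loss. Completers are taken as 44 × 0.75 = 33.

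**The plan's own figure.** 2 × (16 × (1.960 + 1.282) / 12)² = 37.4, which matches 37. This is the per-group formula for two independent groups. In a cross-over it is equivalent to a within-subject difference with SD 16 × √2 = 22.6. It uses no baseline and no within-subject correlation, so the sizing does not settle which variable is analysed. If 16 were already the SD of the within-subject difference, the requirement would be (16 × 3.242 / 12)² = 18.7, or 19 subjects.

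**Variances.** Take each subject's phase 2 minus phase 1 difference, at baseline and at week 10. Assume both have variance V and correlation c. Then:

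- end-of-phase values: V
- change: 2V(1 − c)
- adjusted: V(1 − c²)

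So adjusted/change = (1 − c²) / [2(1 − c)] = (1 + c)/2, which is below 1 for every c below 1. Adjusted/end = 1 − c². The documents do not give c, so a range is shown.

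| c | adjusted/change | adjusted/end |
|---|---|---|
| 0 | 0.50 | 1.00 |
| 0.2 | 0.60 | 0.96 |
| 0.5 | 0.75 | 0.75 |

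Estimating the slope multiplies the adjusted variance by 1 + 1/(n − 4) = 1 + 1/29 = 1.034 at 33 completers. With that cost, adjustment beats change if c < 0.93 (2/1.034 − 1) and beats end values if c > 0.18. At c = 0.3 its variance is 0.91 × 1.034 = 0.94 of that of end values.

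**Power for 12 mg/dL.** Assumptions: 33 completers split 17/16, non-central t, and 22.6 as the SD of the difference in change. The standard error of the beer effect is SD × ½ × √(1/17 + 1/16) = SD × 0.174.

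- Change: 22.63 × 0.174 = 3.94. 12/3.94 = 3.05 on 31 df gives 84%.
- Adjusted, c = 0: V = 22.63²/2, so the end-value SD is 16.0. With the small-sample factor the adjusted SD is 16.27 and the standard error 2.83. 12/2.83 = 4.23 on 30 df gives 98%.
- Adjusted, c = 0.2: the same steps give a standard error of 3.11 and 96%.
- Adjusted, c = 0.5: standard error 3.47 and 92%.
- Plain end values for the same c: 99, 96 and 84%.

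If 16 is instead the SD of the within-subject difference, change already has about 99% power.

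**Carry-over.** Suppose a fraction f of the week-10 beer difference is still present at the phase 2 baseline and none of it at the end of phase 2. The sequence contrast in the baseline difference is then −f times the beer effect, against +2 times in the week-10 difference. Change estimates (1 + f/2) times the effect, and adjustment (1 + cf/2) times. At c = 0.5 and f = 0.2 (assumed) these are 1.10 and 1.05. Neither creates a difference when the beers are equal.

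**The case against.** The strongest reply has three parts.

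*The outcome is already named.* Change is the stated main outcome, each phase has a baseline and an end visit, and a difference in levels is ordinary wording for a difference in change. This largely stands. It is why the point is put as a gain in precision over the named outcome, with the missing visits and baseline role as the gap to close.

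*Plain end-of-phase values would do nearly as well.* This also stands for small c. Adjusted against end values, power is 98 v 99% at c = 0 and 96 v 96% at c = 0.2. The advantage of 92 v 84% at c = 0.5 requires an end-value difference SD of 22.6. With a level SD of 16, that means no correlation between a person's glucose in the two phases, which is unlikely in a cross-over. The firm gain is over change.

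*The regression loses subjects.* Anyone missing one of the four values drops out, and the plan expects 25% loss. This is a real cost against end values. A complete-case comparison of changes needs the same four values.

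A reader might go further and infer that the plan will compare all six visits with Bonferroni correction over 15 pairs, because it says "multiple comparisons will be made by using the Bonferroni correction for normally distributed variables or the Wilcoxon test for paired samples". The documents do not support this: the stated factor is the beers, and the wording may be generic. A reader might also infer that the choice between change and end values is free, with an inflated false-positive rate. Since change is the named outcome, picking end values after seeing the data would depart from the plan; the plan does not invite it.

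**Conclusion.** The point holds as an improvement that should be made. Under the natural reading, the change analysis has a larger variance than the baseline-adjusted one for every c below 1 in large samples, and for c below 0.93 at 33 completers. In power the gain is from 84% to between 92 and 98% for c from 0.5 down to 0, if the difference in change has an SD of 22.6 mg/dL. It is immaterial if 16 mg/dL is already the within-subject SD, and the plan does not say which. The result rests on an assumed c and on equal variances of the baseline and week-10 differences.

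Two further inferences are not supported. First, the rank tests that the plan names cannot carry the order term, but calculation shows that this matters little: 2 to 6% false positives under assumed period effects of 5 to 10 mg/dL. Second, the washout is justified by adherence ("There is a washout period between both phases to facilitate adherence to nutritional intervention"), which might suggest that glycated haemoglobin needs its own analysis. The documents give no data on carry-over, so they support only stating the assumption.

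**What to change.** Before unblinding, define the primary glucose analysis as one between-beer contrast at the end-of-phase (week-10) visit:

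- Regress each subject's phase 2 minus phase 1 week-10 difference on sequence group and on the phase 2 minus phase 1 baseline difference.
- Take the beer effect as half the adjusted sequence contrast. The intercept takes up the period effect.
- Report change from phase baseline as a sensitivity analysis.
- Treat the intermediate visits ("Intermediate phase 1 visit: Clinical, biochemical, dietary, physical activity and anthropometric data are assessed", and likewise in phase 2) as secondary, outside the primary test.
- State the assumption of negligible carry-over into the phase 2 baseline.

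The cost is plan wording and one degree of freedom, about 3% of variance. Subjects missing any of the four values leave this model, so their number should be reported. No new measurement or visit is needed, and the washout is unchanged. If the sponsor prefers change or plain end values, the same paragraph should name that choice, the visit and the single contrast.

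### The 37 subjects required, the 25% loss and the final 44 do not agree: 44 less 25% leaves 33, and 44 can absorb a loss of at most 15.9% if 37 are to remain.

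*Combined protocol and SAP*

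**What the plan says.** The sample-size paragraph of the Statistical analysis plan takes the change in glucose as the main outcome, "whose clinical variability is estimated at 16 mg/dL in pre-diabetic population". The target effect is given as "It was expected to find a difference of 12 mg/dL in glucose levels between two intervention" arms, with a two-sided 5% significance level and "90% of statistical power". The result is reported as "by obtaining a sample size of 37 subjects". The next sentence makes the allowance for attrition: "It was estimated a 25% loss rate, so final sample was 44 subjects".

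The Brief Summary repeats the final number ("We include 44 subjects who are randomized to consume for 10 weeks"), and the Study Detailed Description also gives 44. Neither section offers another loss rate, another base number or another route to 44.

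**The concern.** The plan presents 44 as the consequence of 37 and a 25% loss, but neither usual way of allowing for dropout gives 44. The stated 90% power is attached to 37 subjects, while the plan's own loss rate implies 33. The three numbers cannot all be right, so it is unclear whether the trial was planned for 37 completers with a misprinted loss rate, or for 25% loss with fewer completers and possibly less power than stated.

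Attrition is a real issue in this design. A subject contributes a within-subject comparison only after two 10-week phases separated by a 4–8 week wash-out, and the Study Detailed Description itself expects 20 uninterrupted weeks to be hard on participants.

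**Working it through.** **Inputs** (all from the Statistical analysis plan): Zα = 1.960 two-sided, Zβ = 1.282, variability 16 mg/dL, difference 12 mg/dL, required number 37, loss 25%, final number 44.

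**Step 1: reproduce the 37.** The plan prints no formula. The usual two-mean formula gives

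n = 2 × (1.960 + 1.282)² × 16² / 12² = 2 × 10.51 × 256/144 = 37.37.

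This matches the stated 37, although strict rounding up would give 38. The base number is therefore not where the problem lies.

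**Step 2: go from 37 to the final number.**

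| Calculation | Result |
|---|---|
| 37 / (1 − 0.25) | 49.3, so 50 |
| 37 × 1.25 (under-inflates) | 46.25, so 47 |
| 44 × (1 − 0.25) | 33, which is 37 − 4 |
| 1 − 37/44 | 15.9% |

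Rounding 46.25 down gives 46, so rounding does not explain 44. Two other percentages would: a 15% loss by division (37/0.85 = 43.5, so 44) or a 20% add-on (37 × 1.20 = 44.4). The plan states neither, so these are only guesses at the origin.

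**Step 3: what four fewer completers cost.** This depends on the SD of the within-subject difference between beers, which the plan does not give. The formula in step 1 is either the number per group for two independent groups, or the total for a cross-over in which 16 mg/dL is the SD in each period and the within-subject correlation is zero. In the second reading the SD of the difference is 16 × √2 = 22.6 mg/dL. On that SD:

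| Completers | Power for 12 mg/dL, normal | Power, paired t | Difference detectable with 90% power, normal | Same, paired t |
|---|---|---|---|---|
| 37 | 89.7% | 88.1% | 12.1 mg/dL | 12.4 mg/dL |
| 33 | 86.1% | 84.0% | 12.8 mg/dL | 13.2 mg/dL |

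**Step 4: range over the unstated correlation.** With 33 completers, 16 mg/dL per period and an assumed correlation r, the SD of the difference is 16 × √(2(1 − r)):

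| r (assumed) | SD of difference | Power, normal | Power, paired t |
|---|---|---|---|
| 0 | 22.6 mg/dL | 86.1% | 84.0% |
| 0.17 | 20.6 mg/dL | 91.7% | 90.0% |
| 0.3 | 18.9 mg/dL | 95.4% | 94.2% |
| 0.5 | 16.0 mg/dL | 99.1% | 98.7% |

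By the normal approximation, 90% is kept with 33 completers up to an SD of 12 × √33 / 3.2415 = 21.3 mg/dL, which is r = 1 − 21.27²/512 = 0.12. By the paired t the limit is 20.6 mg/dL (r = 0.17).

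The last row also covers the case where 16 mg/dL is itself the SD of the difference. The number required would then be 10.51 × 256/144 = 18.7, so 19 by the normal approximation or 21 by the paired t. In that case 33 is ample.

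**The case against.** The strongest reply is that no harm is shown. The loss of about four power points arises only at zero within-subject correlation, the least favourable row of the table above. A correlation of 0.17 or more restores 90% with 33 completers on either calculation, and even the zero-correlation case leaves 84–86%. Nothing about visits, products or analyses changes. The plan also states both a required number and a power, so if only the percentage is misprinted, 37 completers and 90% stand as written. Finally, because no formula is printed, the 22.6 mg/dL is a reading of the 37 and not an assumption that the plan declares.

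Most of this is fair as a limit on the consequence. The power loss is conditional, 22.6 mg/dL is an inferred value, and 33 is the number implied by a planning assumption, not an observed count. None of it reconciles 37, 25% and 44. The reassuring rows need a correlation that the plan does not state, and the misprint explanation needs a loss rate that appears nowhere in the documents.

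**Conclusion.** The concern holds. At the stated 25% loss, 44 randomised subjects leave 33 and not 37; a 25% loss calls for 50 (or 47 by the cruder rule), and 44 tolerates at most 15.9%. This part is pure arithmetic on the plan's own figures.

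The effect on power is not settled by the documents. It ranges from a fall of about four points, if the between-beer difference has an SD of 22.6 mg/dL, to no practical effect, if that SD is 16 mg/dL. The correlations used to span this range are assumptions. The error should be fixed because it sits in the sample-size justification; its likely consequence is modest.

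**What to change.** Keep 44 and make the three numbers agree in one of two ways:

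- if a loss of about 16% was meant, correct the percentage, which leaves 37 completers; or
- if 25% was meant, state that 33 completers are expected.

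The sponsor should choose according to what was actually planned, and not fit the percentage to the 44. Then give one power figure for that number of completers and name the SD of the between-beer difference on which it rests. If that SD is 22.6 mg/dL, the figure for 12 mg/dL is 86% (normal) or 84% (paired t) with 33 completers, and 90% or 88% with 37. If the sponsor has a smaller SD, report only the value computed from it.

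The cost is two sentences in the Statistical analysis plan, with no extra subjects and no change to procedures or analyses. The one drawback is that the stated power may come out a little lower if the SD is near 22.6 mg/dL.
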